We completed pre-clinical exercise-induced shoulder injury ($n = 190$) and clinical post-operative shoulder pain ($n = 150$) cohort studies. We have presented findings at national ($n = 4$) and international ($n = 3$) scientific conferences and disseminated results in high quality journals ($n = 11$ published, with $n = 3$ review). We made notable progress towards our overall goal of developing personalized musculoskeletal pain interventions by identifying and validating a high-risk subgroup comprised of *COMT* genotype and pain catastrophizing. This high-risk subgroup predicted: a) heightened pain responses following exercise-induced shoulder injury, and b) poor post-operative shoulder pain outcomes. Below is a summary of key findings supporting our renewal:

Exercise-Induced Shoulder Injury as a Pre-Clinical Model for Clinical Post-Operative Shoulder Pain: The use of exercise-induced injury in humans was motivated by the difficulties and challenges with non-human animals as pre-clinical models in pain research.^{38, 39} One feature enhancing the translational potential of exercise-induced injury is that it produces prolonged pain (mean days = 6.1, $sd = 1.8$), which is unique among experimental methods of inducing pain in humans (where duration is measured in seconds or minutes).⁴¹⁻⁴³ This is important because long duration is the defining characteristic of chronic pain. Furthermore, there was overlap in pain intensity and disability reports between the pre-clinical and clinical participants' pre-operative ratings (Figure 2). Additional evidence supporting this pre-clinical model came from analyses reported in the peer-review literature regarding similarities in endogenous pain modulation^{45, 46} and that a specific psychological factor, pain catastrophizing, was a predictor of pain outcomes for both cohorts.^{16, 47} These data supported the validity of this pre-clinical model and provided direction for future analyses.

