
[figure not shown]
C2. Overview

Potential subjects will be screened and those meeting the high-risk criteria will be randomized into intervention groups. Treatment conditions will be administered for four consecutive days and statistical analysis will determine whether the combined personalized intervention group experienced shorter shoulder pain duration, lower peak pain intensity, or decreased upper-extremity disability (Aim #1) and determine which molecular, psychological, and pain sensitivity regulation mechanisms are associated with pain relief (Aim #2).

C3. Procedures

An overview of BISP study procedures is presented in Figure 5, and then described in more detail.

Figure 5. BISP Timeline and Study Procedures

Risk Subgroup Screening. We propose to enroll 448 high-risk participants, which will require prescreening approximately 3,000 people. In order to accomplish this we will conduct quarterly large-scale screenings on campus and in the local community (e.g. at local shopping malls, supermarkets, and community events) on a quarterly basis. We anticipate screening at least 200 people at each event for the first 4 years of the award (15 events total). At each screening, after providing informed consent, the participant will complete a brief screening questionnaire to determine eligibility and will be asked for permission to recontact. Members of the BISP team (Drs. [name] and [name]) have prior experience on screening this volume of participants

through their work on the Orofacial Pain Prospective Evaluation and Risk Assessment (OPPERA) study.⁵⁴ Eligibility will be determined from established inclusion and exclusion criteria from our initial funding period that establish appropriateness for the exercise-induced injury protocol, now modified to account for the risks of administering propranolol. Details of the inclusion and exclusion criteria are reported in the Human Subjects section. If eligible, each participant will provide a saliva sample and complete the Pain Catastrophizing Scale (PCS), a 13-item, 4-point rating scale.^{55, 56} A small incentive (\$5 gift card) will encourage participation. We have had success with similar approaches in the past for OPPERA.

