
Randomization. There are reported sex differences in pain conditions,^{58, 59} and we have observed that females report higher pain sensitivity in our studies of shoulder pain.⁶⁰ Sex differences in how *COMT* impacts pain sensitivity has also been described, with females having a stronger association with pain sensitivity for certain genetic variants.⁶¹ Therefore randomization will be balanced to ensure equal allocation for males and females in the different intervention groups (i.e. sex stratified). The randomization scheme will be prepared by computer and completed prior to the start of the study. After the randomization list is generated treatment assignments will be contained in sealed, numbered envelopes. Envelopes will be opened in sequential order as each participant enters the study by research staff blinded to application of interventions (i.e. treatment assignment and allocation will be by different research personnel). We will randomize prior to muscle injury to ensure propranolol is absorbed by the system before muscle injury. Propranolol administration before injury allows for any immediate pre-emptive effects on the molecular or pain sensitivity regulation measures to be detected during the baseline session (Figure 5). This administration also matches when propranolol would be administered in a clinical model (i.e. pre-operatively) so that translational component will be maintained.

Exercise-Induced Shoulder Injury. Research personnel performing the muscle injury protocol will be blinded to randomization results. Subjects will undergo exercise-induced shoulder injury to the dominant arm. The

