
C4. Statistical Analysis Plan

All statistical analyses will be performed using the SAS software, version 9 (SAS Institute Inc, 1996). Summary statistics will be provided for baseline measures by intervention groups to determine if randomization produced balanced groups. Any group imbalance will be investigated further to determine if covariates should be considered. For Specific Aim #1, our primary analysis for efficacy will compare shoulder pain duration (i.e. *number of days until subject rated their current pain at 0/10 and their worst pain was rated less than 2/10*) across the four randomly assigned groups with the use of logistic regression. Consistent with the initial funding period, the primary outcome variable will be dichotomized based on duration of at least 7 days or not. There is an *a priori* plan to include age, sex, and race as covariates in this analysis, additional variables will be added as covariates only if imbalanced across groups and correlated with outcome measures. We anticipate very little missing data because this is a pre-clinical study, but any missing outcomes will be predicted by subject pain intensity trajectory plus baseline demographic factors. The primary comparison between the combined personalized intervention and the combined placebo condition will be tested at the 0.05 significance level, while the other five between group contrasts will be tested using a step-down procedure. For the other primary outcomes (peak pain intensity and upper-extremity disability as continuous measures) we will perform a similar analysis process (i.e. same considerations for post randomization imbalance, covariates, and missing data) with linear regression analysis to compare the four intervention groups. For Specific Aim #2, we will fit path models with predetermined orders to investigate the direct (intervention group) and indirect effects (through the mediating psychological, molecular, and pain sensitivity paths) of the randomly assigned condition on pain relief. The combined placebo intervention will serve as reference group for these analyses. The total, direct and indirect mechanistic effects on pain duration (dichotomous) and peak pain intensity and upper-extremity disability (continuous) will be estimated and tested at the 0.05 significance level for the comparison of assigned conditions. Specifically, the total effect will be estimated and tested through a logistic regression for pain duration and a general linear model for peak pain intensity, both of which include the assigned intervention conditions as independent variables while controlling for participant age, sex, and race. The direct effect will be estimated and tested with the use of the same models including the same independent variables, but controlling for mediating molecular, psychological, and pain sensitivity variables in addition to age, sex and race. The two regression models in the second step will reveal the contributions of the mediating psychological, molecular, and pain sensitivity variables on pain relief. On the other hand, the indirect effect will be calculated based on the difference between the total and direct effects. In addition, we will conduct a third

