
set of regression analyses to evaluate the effect of the assigned condition on the mediating variables which will determine which indirect paths are statistically significant.

C4. Sample Size Estimate and Study Timeline

A total of 448 high-risk subjects will be recruited. In the initial funding period we found that 40.5% of high risk subjects had pain duration \geq 7 days while 21.4% of the low risk group had long duration (Table 1). In our power analysis, we assumed that 40% of the combined placebo group will have long pain duration (rate for high risk subgroup), while the rate for the combined personalized intervention group will be 20% (rate for low risk group). Those with one personalized intervention were assumed to have 30% chance of having duration \geq 7 days. The planned sample size will enable us to have 80% power to detect the assumed differences across the four intervention groups and 91% power for the primary comparison between the combined personalized and the combined placebo interventions at a type-I error level of 0.05. The overall BISP timeline is in Table 3.

Table 3. Timeline and Key Periodic Events for BISP

Year 1		Year 2		Year 3		Year 4		Year 5					
Start Up	Quarterly Meetings with Research Team Annual Progress Reports to Institutional Review Board, Data Safety Monitoring Body, and NIH												
	Screening, Recruitment (annual rate = 96-120 participants), Intervention, and Follow Up												
	Scientific Conference		Scientific Conference		Scientific Conference		Scientific Conference		Scientific Conference				
On Site Consult		On Site Consult		On Site Consult		On Site Consult		On Site Consult	Analysis, Dissemination				

C5. Potential Pitfalls and Alternative Approaches

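### The screening PCS score, held for every participant before randomization, should be a fixed covariate rather than one admitted only if imbalanced and correlated with outcome

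*Combined protocol and SAP*

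**What the plan says.** C3 (Procedures, Risk Subgroup Screening) has PCS scored at the screening event: "each participant will provide a saliva sample and complete the Pain Catastrophizing Scale (PCS", and a score of 5 or more is required for high-risk status. Only those who qualify are then randomized (C2), so the score exists for every participant and precedes both allocation and the first dose. The account of the initial funding period states that "a specific psychological factor, pain catastrophizing, was a predictor of pain outcomes for both cohorts".

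The Statistical Analysis Plan (the first of two sections numbered C4) names age, sex and race as covariates for the logistic model of pain duration of at least 7 days. For anything else, "additional variables will be added as covariates only if imbalanced across groups and correlated with outcome measures". The same treatment of covariates carries over to the linear models for peak pain and upper-extremity disability. The plan gives no imbalance test, correlation cut-off, list of candidate variables, or timing relative to unblinding.

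For Aim 2, the total-effect and direct-effect models also list age, sex and race, and the direct-effect model adds the mediators. PCS is one of the psychological mediators, but screening PCS is not named as a covariate in any of these models. The regressions of mediators on condition are mentioned without covariates, and without saying whether the response is the raw score or the change from baseline.

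**The concern.** A baseline measure that the investigators regard as prognostic, already collected in everyone and out of reach of treatment, is left to enter the model by chance. Baseline-session measures are less clean for this purpose, because the first propranolol dose is deliberately given early enough to act on them.

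Two things are at stake. One is efficiency: variance in the continuous outcomes and in the PCS mediator that could be removed for nothing. The other is pre-specification: two analysts following the rule could reach different models for the same primary comparison, because neither condition is defined. For the odds ratio this also means that the data decide whether the reported effect is conditional on PCS.

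**Working it through.** **Inputs from the documents.** "A total of 448 high-risk subjects will be recruited". With an equal split over four arms (implied by "randomization will be balanced to ensure equal allocation for males and females in the different intervention groups" but not stated as a ratio), that is 448/4 = 112 per arm. Rates of duration of at least 7 days: "we assumed that 40% of the combined placebo group will have long pain duration"; 30% in each single-intervention arm; 20% in the combined personalized arm. Alpha is 0.05, taken as two-sided.

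**The plan's own figures.**
- Primary contrast, pooled two-proportion test: [0.20 − 1.96·√(2·0.3·0.7/112)] / √((0.24 + 0.16)/112) = (0.20 − 0.120)/0.0598 = 1.34, giving power 0.910 against the stated 91%.
- Four-group test, 3 df: noncentrality 112·(0.01 + 0 + 0 + 0.01)/(0.3·0.7) = 10.67, giving power 0.790 against the stated 80%.

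Both reproduce without any covariate, so the sample size does not rest on PCS adjustment.

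**Assumption needed.** The documents give no slope of outcome on PCS within PCS of 5 or more. Its strength is therefore assumed below and shown as a range.

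**Continuous outcomes (peak pain, QuickDASH).** With correlation r beyond age, sex and race, residual variance falls by r² and the equivalent total is 448/(1 − r²).

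| r | variance removed | equivalent N | extra subjects | 80% power becomes |
|---|---|---|---|---|
| 0.1 | 1% | 452 | 1% | 80.4% |
| 0.2 | 4% | 467 | 4% | 81.6% |
| 0.3 | 9% | 492 | 10% | 83.6% |
| 0.4 | 16% | 533 | 19% | 86.4% |

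**Logistic primary outcome.** Simulation of the two-arm primary contrast: 112 per arm, marginal rates 40% and 20%, one standard-normal covariate, 10,000 runs per setting, Monte Carlo error about 0.003. Age, sex and race were not modelled. For the plan's rule, both imbalance and correlation were judged at p < 0.05, an assumption because the plan gives no threshold.

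| odds ratio per SD | unadjusted | PCS always in | plan's rule | PCS enters under rule |
|---|---|---|---|---|
| 1.0 | 0.910 | 0.910 | 0.909 | 0.4% |
| 1.25 | 0.909 | 0.912 | 0.908 | 1.6% |
| 1.5 | 0.910 | 0.919 | 0.911 | 3.9% |
| 2.0 | 0.903 | 0.926 | 0.906 | 5.0% |
| 2.5 | 0.908 | 0.945 | 0.912 | 5.6% |

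Loosening the imbalance test to p < 0.20 raises entry to about 20% at odds ratios of 2.0 and 2.5, with power 0.910 and 0.922, still below fixed adjustment.

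The gain is not a smaller standard error. At an odds ratio of 2.0 per SD, the standard error of the log odds ratio rises from 0.308 to 0.327 while the estimate moves from −0.994 to −1.094. The ratio of estimate to standard error goes from 3.23 to 3.35. The treatment odds ratio shifts from e^−0.994 = 0.37 to e^−1.094 = 0.33 because it is now conditional on PCS.

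Under the null, rejection under the rule was 0.043 to 0.050 across all settings.

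**PCS mediator regressed on condition.** Assume a correlation of 0.5 to 0.7 between screening PCS and later PCS.
- Against an unadjusted raw-score model: r² = 0.25 to 0.49 of residual variance is removed, and 1/(1 − r²) = 1.33 to 1.96, or 33 to 96% more subjects.
- Against a change-score model with equal variances: 2(1 − r)/(1 − r²) = 2/(1 + r) = 1.33 at r = 0.5 and 1.18 at r = 0.7, or 33% down to 18% more subjects.

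**The case against.** The strongest objection is that PCS may predict little among those enrolled. The statement about both cohorts carries no effect size. Table 1 tests only joint genotype-and-PCS subgroups, and every participant here lies on the same side of the rs6269 AA and PCS cut. Subgroups combining PCS of 5 or more with the other three genes did not predict duration (p = 0.228, 0.291 and 0.280), and for IL1B the rates ran the other way (20.8% against 27.9%). Truncation at 5 narrows the range and tends to lower correlations. All of this stands. A reader might infer that PCS is established as prognostic in this population; the documents do not show it.

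A reader might also infer that the primary comparison is underpowered or imprecise without PCS. It is not: the stated power reproduces unadjusted, the simulated gain is small, and the standard error of the log odds ratio does not fall. Nor should the rule's dependence on the data be read as inflating type I error. The simulated one-covariate rule was neutral to slightly conservative; selection among many candidates was not simulated.

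Finally, the largest figures concern an Aim 2 regression whose form is unstated. If change from baseline is intended, part of that gain is already taken.

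What the objection does not remove is that the primary models are left open by an undefined rule, and that fixing PCS in them loses almost nothing if it turns out to be unprognostic (0.910 in both columns at an odds ratio of 1.0).

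**Conclusion.** The point holds as a modest weakness of efficiency and pre-specification, not as a threat to validity or to the sample size. On the documents' own account PCS is a natural baseline covariate, and the rule, which demands both imbalance and correlation, would usually leave it out. How usually depends on thresholds that the plan does not give.

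The benefit is smallest for the dichotomized primary outcome, more useful for the two continuous outcomes, and potentially largest for the PCS mediator regression. Every size rests on assumed associations, and the Aim 1 gains could be near zero. The absence of a fixed model for the three primary outcomes does not depend on those assumptions.

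**What to change.** In the Statistical Analysis Plan (C4), list the screening PCS score, as a continuous variable, with age, sex and race as a fixed covariate whatever the observed balance:

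- in all three Aim 1 models;
- in both the total-effect and the direct-effect models of Aim 2, since the indirect effect is taken as their difference and the two should share the same baseline covariates;
- in the regression of the PCS mediator on condition, stating there whether the response is the raw score or the change.

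Confine the imbalanced-and-correlated rule to a sensitivity analysis. State that the primary odds ratio is conditional on PCS as well as on age, sex and race.

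The cost is one line of text and one degree of freedom per model. No new data are needed.

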Primary Outcome Measures. The primary outcome measures were selected based on relevance to the clinical model and successful use in the initial funding period. Pain intensity ratings and self-report of upper-extremity disability will be used as primary outcome measures to determine efficacy for shoulder pain duration, peak shoulder pain intensity, and peak upper-extremity disability. ***These constructs have a conceptual link to chronic pain¹ and therefore can be used to characterize the presence of persistent or continued pain following exercise-induced injury.*** The Brief Pain Inventory (BPI) will be used to measure pain intensity as it has been found to have good test-retest reliability over short intervals.⁹⁷ The BPI consists of rating pain intensity on an 11-point numerical rating scale ranging from 0 (no pain) to 10 (worst pain intensity imaginable). The BPI asks subjects to rate current pain and pain at its worst, best and average over the past 24 hours. ***To determine recovery, subjects will complete the BPI daily until they rated their current pain at 0/10 and their worst pain was rated less than 2/10. The number of days it took to reach this recovery criterion will be recorded as duration of shoulder pain.*** The highest worst pain intensity recorded during recovery will be recorded as the peak shoulder pain intensity. The Disabilities of the Arm, Shoulder, and Hand Questionnaire (DASH) will be used to assess upper-extremity disability and we will continue to use a validated abridged version of the DASH (the QuickDASH) which consists of 11 functional items, with total scores ranging from 0 (not disability) to 100 (complete disability).⁹⁸ We will use the QuickDASH because shoulder pain can also affect distal function of the arm and hand, and we wanted to obtain a global upper-extremity assessment. Similar to the BPI ratings, QuickDASH scores will be recorded daily until recovery and the highest score during this period will be recorded as peak upper extremity disability. Another advantage of these measures is they are widely accepted as primary outcome measures in clinical studies, and were used as such in the initial funding period. Therefore, these measures will allow for specific effect size estimates for a subsequent randomized clinical trial in post-operative shoulder pain.

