1) *Feasibility of Proposed Sample Size.* In the initial funding period we recruited 340 subjects. There is potential for higher recruitment rate in this proposal because it involves only the exercise-induced injury cohort of healthy volunteers. Recruiting for the clinical cohort was much more time intensive. Drs. [name] and [name] have experience in large scale recruitment from OPPERA⁵⁴ and our planned screenings will generate sufficient high-risk participants. The protocol requires at least five days of participation from participants and we had an outstanding completion rate (189/190) during the initial funding period. Therefore, retention and missing data are not expected to be a concern. If there is more missing data than anticipated we will account for it in our statistical analysis. 2) *Lack of Shoulder Specific Intervention Pilot Data.* Pilot data demonstrating effect sizes will be vital when proposing a clinical trial in the post-operative setting. This renewal proposal includes established pharmaceutical⁸ and psychological⁸⁶ interventions that have demonstrated effects in clinical populations (orofacial and low back pain respectively) from studies conducted by members of this research team. We will monitor intervention responses for expected results on process variables and adjust the intervention components if indicated. 3) *Low Risk Subgroup.* Intervention effects for low risk subjects will be unknown, and these effects potentially have scientific interest. However the pragmatic advantages of greater research design efficiency and direct relevance to clinical investigations justified focus on the high risk subgroup. 4) *Exploratory Analyses.* We intentionally presented a focused statistical analysis plan to determine the efficacy (Aim #1) and mechanisms (Aim #2) of the personalized interventions described in this proposal. We do acknowledge that response to these interventions may not be as predictable as we have hypothesized. In the unlikely event that the Aim #1 analyses indicate no group differences we will perform additional analyses to inform future research in this area. For example as already mentioned, there is potential for sex differences in pain sensitivity⁵⁸⁻⁶⁰ and COMT variant influence on pain sensitivity⁶¹ to impact study results. We have accounted for this with stratified randomization based on sex and by *a priori* including sex as a covariate in primary analyses. In the case of null findings, however, a specific exploratory analysis will determine if sex-specific intervention effects occurred. For Aim #2 other analyses will be more exploratory in nature (e.g. post-hoc treatment responder) and will be enhanced by the storage of excess DNA, plasma, and RNA so additional genetic predictors and molecular mechanisms can be considered (assuming subjects consent for that use).

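### The rule for predicting missing primary outcomes does not list the assigned arm, so any imputed values can pull the arm comparison toward zero

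*Combined protocol and SAP*

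**What the plan says.** The primary endpoint is pain lasting at least 7 days, compared across four randomised groups by logistic regression with age, sex and race as covariates (C4, Statistical Analysis Plan). The same section gives the only concrete rule for missing data: "any missing outcomes will be predicted by subject pain intensity trajectory plus baseline demographic factors". It carries the same missing-data approach over to peak pain and disability, so the rule covers all three primary outcomes. It does not say whether prediction is single or multiple, how many ratings are needed, or what happens if there are none. No sensitivity analysis is named.

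On the amount of missing data, C4 says "We anticipate very little missing data because this is a pre-clinical study". Item 1 of C5 adds "we had an outstanding completion rate (189/190) during the initial funding period", and then "If there is more missing data than anticipated we will account for it in our statistical analysis".

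On timing, the Randomization paragraph of C3 says "We will randomize prior to muscle injury to ensure propranolol is absorbed by the system before muscle injury", and the pharmaceutical paragraph of C3 also puts the first dose before the injury. The Exercise-Induced Shoulder Injury paragraph of C3 says the reverse: that the fatigue protocol precedes randomisation. Duration is defined by daily ratings up to a recovery criterion: "The number of days it took to reach this recovery criterion will be recorded as duration of shoulder pain".

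**The concern.** An imputation model that leaves out a variable used in the analysis treats that variable as unrelated to the outcome, given the predictors that are kept. Here the variable left out is the one under test. A participant who leaves the combined personalised arm after one or two ratings and a similar one who leaves the combined placebo arm would receive much the same predicted risk. The comparison is then diluted in proportion to the amount imputed.

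Two gaps make the rule harder to apply. The fallback in C5 leaves the method open until the amount of missing data is known. And if randomisation and the first dose do come before the injury, someone could be randomised and then stop before it. That person has no post-injury trajectory, so prediction would rest on demographics alone. If such a person were nevertheless rated, pain of 0/10 would satisfy the recovery criterion as literally worded. The plan does not say how such a participant enters the analysis.

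**Working it through.** **Inputs.** From C4 (Sample Size Estimate and Study Timeline): "A total of 448 high-risk subjects will be recruited"; assumed rates of long duration of 40% (combined placebo), 30% and 30% (single interventions) and 20% (combined personalised); type I error 0.05; stated power 91% for the primary comparison and 80% across four groups. Assumptions: 112 per arm (448/4, since no numeric allocation ratio is given) and a two-sided test.

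**Reproducing the plan's figures.** With a pooled-variance test,

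power = Φ{[Δ − 1.96·√(2p̄(1−p̄)/n)] / √([p₁(1−p₁)+p₂(1−p₂)]/n)}.

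For p₁ = 0.40, p₂ = 0.20, p̄ = 0.30 and n = 112, this is Φ{(0.20 − 1.96×0.0612)/0.0598} = Φ(1.34) = 91.0%, which matches the stated 91%. The four-group chi-square test has noncentrality 112×(0.10²+0.10²)/0.21 = 10.67 on 3 df and power 79.0%, in line with the stated 80%.

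**Worst-case dilution.** Suppose a fraction m is missing in every arm, those missing have the same risks as the rest of their arm, and the ratings they left carry no information. Arm-free prediction then gives everyone the all-arm mean, (40+30+30+20)/4 = 30%:

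- placebo: (1−m)×0.40 + m×0.30 = 0.40 − 0.10m
- combined: (1−m)×0.20 + m×0.30 = 0.20 + 0.10m
- difference: 0.20×(1−m)

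The fair comparator is a method that includes arm at the same m. When ratings carry no information, this is approximately unbiased rates of 40% and 20% with n = 112(1−m). The documents give no m for this trial, so a range is shown; only the first row has a basis in them (1/190).

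| m | Missing of 448 | Difference, arm omitted | Power, arm omitted | Power, arm included |
|---|---|---|---|---|
| 0.53% | 2.4 | 19.9 points | 90.7% | 90.8% |
| 2% | 9.0 | 19.6 points | 89.8% | 90.4% |
| 5% | 22.4 | 19.0 points | 87.9% | 89.5% |
| 10% | 44.8 | 18.0 points | 84.1% | 87.8% |

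At 10% missing, the fall from 91.0% to 84.1% is 6.9 points. Of this, 91.0 − 87.8 = 3.2 points are lost information that no method recovers, and 87.8 − 84.1 = 3.7 points come from leaving out arm. At 5% the part due to leaving out arm is 89.5 − 87.9 = 1.6 points.

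**When the trajectory is informative.** If it carries half of the arm effect, the difference is 0.20×(1 − m/2), or 19.0 points rather than 18.0 at 10% missing. A large-sample simulation with an assumed early pain signal gave, at 10% missing, from about 18 points (no arm effect in the signal) to about 19.5 points (a strong signal carrying most of it).

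**Type I error.** With a common true rate of 30%, 10% missing and a single random draw per missing outcome, simulation gave about 5% for the primary comparison when arm is left out, and between 7% and 8% when arm is included but only one draw is made.

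**The case against.** The strongest reply is that this will hardly matter. The only retention figure in the documents is 189 of 190, which would leave two or three participants in 448 to impute. The trajectory is recorded after randomisation, alongside treatment, so it carries part of any arm effect. Any residual bias is toward no difference. And arm is unlisted in a brief sentence, not expressly excluded. All of this stands, and it limits the size of the point. It does not remove it: the rule as worded is the one a programmer would follow, and the retention figure comes from a cohort without this trial's drug dosing and daily interventions.

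Three stronger readings are tempting, and the documents do not support them.

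- A reader might infer that the plan chose single imputation and so overstates precision. The text says only that outcomes will be predicted. Even a single draw without arm kept type I error near 5% in the simulation above.
- A reader might infer that uninjured participants will be scored as recovered. No text directs this, and the case cannot arise at all if the fatigue protocol precedes randomisation.
- A reader might infer that stops before injury would be more common on propranolol and so favour the drug arms. Nothing in the documents gives such a rate or direction.

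**Conclusion.** The point holds as a cheap improvement to the specification. The stated rule leaves the assigned arm out of the prediction of all three primary outcomes. In the worst case this shrinks the primary difference by the factor (1−m) and costs, relative to including arm, about 0.6 points of power at 2% missing, 1.6 at 5% and 3.7 at 10%. At a loss of 1 in 190 it is negligible. These are upper bounds under equal missingness across arms, 112 per arm, the plan's own event rates and uninformative trajectories; the missing fractions of 2% and above are assumptions.

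The issue of participants without post-injury ratings is conditional. It exists on the order given in the Randomization and pharmaceutical paragraphs of C3, and not on the order given in the Exercise-Induced Shoulder Injury paragraph. The conflict has to be settled before the handling can be written.

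**What to change.** - In C4, replace the prediction sentence with multiple imputation that includes assigned arm, sex, age, race and all available daily BPI ratings (screening PCS is optional), combined by Rubin's rules. Once arm is in the model, the imputation must be multiple: the single-draw version inflated type I error in the simulation above.
- Classify directly as 7 days or more, without imputation, anyone whose rating on Day 7 or later still fails the recovery criterion, counting days as for duration.
- Reconcile the three C3 paragraphs on the order of randomisation, first dose and injury. If a randomised participant can remain uninjured, state that such a person is not scored as recovered, say how they enter the primary analysis, and add one sensitivity analysis, for example counting them as 7 days or more.
- Let the open-ended sentence in C5 refer to this rule.

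The cost is SAP wording and standard SAS procedures. Standard errors will be slightly larger than under single prediction. No visit, assessment or sample size changes.
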